### **4.1 Inclusion criteria**

1. Written informed consent must be obtained before any assessment is performed.
2. RRMS patients aged between 18-65 years that fulfill following criteria:
  - d) In non-treated/newly-diagnosed patients with two or more serious attacks within one year or three or more serious attacks within two years and one or multiple gadolinium-enhancing lesions in cranial MRI or with significantly increased T2 lesions compared to the previous MRI.
  - e) In non-responders despite treatment with a beta-interferon or glatiramer acetate with adequate duration and dose, where:
    - a. adequate treatment duration is at least 1 year and,
    - b. non-responders are patients with no changes in attacks or increased number of attacks after one year of treatment, or with more severe attacks, or those with one or multiple contrast enhancing lesions in cranial MRI or where there is an increase in T2 lesions identified with successive MRI's.
  - f) In RRMS patients who are unable to tolerate first-line treatments due to adverse effects associated with parenteral administration.
3. Last relapse of the patient should be at least 2 months before study entry.
4. Last steroid dose of the patient should be at least 1 month before study entry.

5. Last interferon or glatiramer acetate dose of the patient should be at least 1 month before study entry.
6. Last cyclophosphamide, mitoxantrone, teriflunamide, natalizumab and azathioprine dose of the patient should be at least 3 months before study entry.

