**Table 6-1 Assessment schedule for MS Patients**

Visit	1	2	3
Day	0	90±7	180±14
Obtain Informed Consent	X		
Evaluation of Inclusion/Exclusion Criteria	X		
Demographic and Previous Data	X		
Other Concomitant Diseases	X		
MS and Treatment History	X		
Assessment of the MS Relapses Within Last 2 Years	X		
Recording of Relapses			X
Pregnancy Test (Urine)	X		
Varicella-Zoster Ab	X		
Hematology *	X**	X	X
Clinical Chemistry *	X**	X	X
ECG	X		
Optical Cohorence Tomography	X	X	
EDSS Measurements	X		X
PASAT Measurements	X		X
Symbol Digit Modalities Test (SDMT) Measurements	X		X
9-Hole Peg Test	X		X
25 Foot Walk Test	X		X
Collecting Serum and Blood Samples for Biomarker Research	X	X	X
Dispense Study Medication	X	X	
First Dose Administration	X		
End of the Study Visit			X

\* Hematology: Leukocytes, Hemoglobin, Absolute Neutrophilis, Absolut, Lymphocyte, Platelet  
 Clinical Chemistry: AST, ALT, BUN, Creatinine, Total Cholesterol, Tryglicerides, LDL-K, HDL-K, TSH,ST4, Glucose, HbA1c

\*\* If the patient has hematology and clinical chemistry results within the last 1month, the tests do not have to be repeated.

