## **6.1 Information to be collected on screening failures**

Since the study is aiming to collect serum samples from the MS patients and healthy volunteers, screening visit is not applicable. The investigators will assess the inclusion/exclusion criteria in visit 1 and the patients who are not eligible for the study will not give any serum samples. There is no information to be collected for screen failures.

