#### **6.5.1.2 Clinical chemistry**

Blood samples will be collected at screening (Visit 1) and at each scheduled visit to verify a patient's eligibility and will include but not limited to the following parameters: AST, ALT, BUN, Creatinine, Total Cholesterol, Tryglicerides, LDL-K, HDL-K, TSH, ST4, Glucose, HbA1c

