## 8.3 Database management and quality control

Data from the CRFs are entered into the study database by Novartis Data Management staff using single data entry. Verification is performed manually by a separate member of the Data Management staff by comparing the Case Report Form to the data entered into the database.

Data from the CRFs are entered into the study database by Contract Research Organization (CRO) staff following their own internal standard operating procedures that have been reviewed and approved by Novartis.

Subsequently, the entered data are systematically checked by Data Management staff, using error messages printed from validation programs and database listings. Other errors or omissions are entered on Data Query Forms, which are returned to the investigational site for resolution. The signed original and resolved Data Query Forms are kept with the CRFs at the investigator site, and a copy is sent to Novartis so the resolutions can be entered into the database. Quality control audits of all key safety and efficacy data in the database are made prior to locking the database.

Adverse events will be coded using the Medical dictionary for regulatory activities (MedDRA) terminology.

Laboratory samples will be processed centrally and the results will be sent electronically to Novartis (or a designated CRO).

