6.3 LABORATORY TESTS

6.3.1 Clinical Biochemistry

Patients' **AST, ALT, BUN, Creatinine, Total Cholesterol, Tryglycerides, LDL-C, HDL-C, TSH, ST4, Glucose and HbA1c** values will be tabulated by calculating mean and standart deviation and compared as Visit 1 vs. Visit 2 and Visit 1 vs. Visit 3 by using appropriate statistical test. Wilcoxon test will be used in the dependent variables with non-normal distributions whereas Paired sample t test will be used in the dependent variables with normal distributions.

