6.3.2 Hematology

Patients' **WBC, Absolute Lymphocyte Count, Platelet, Absolute Neutrophil Count and Hemoglobin** values will be tabulated by calculating mean and standart deviation and compared as Visit 1 vs. Visit 2 and Visit 1 vs. Visit 3 by using appropriate statistical test. Wilcoxon test will be used in the dependent variables with non-normal distributions whereas Paired sample t test will be used in the dependent variables with normal distributions.

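### Visit 1 haematology and chemistry may be up to a month old, as long as the minimum steroid and interferon/glatiramer washout, yet serve as baseline for the SAP 6.3 paired laboratory tests

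*Protocol*

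**What the plan says.** Protocol Table 6-1 schedules haematology and clinical chemistry at all three visits, but the Visit 1 entry carries a footnote: "If the patient has hematology and clinical chemistry results within the last 1month, the tests do not have to be repeated". Protocol 6.5.1.2 describes collection without that exception: "Blood samples will be collected at screening (Visit 1) and at each scheduled visit to verify a patient's eligibility". Section 6.5.1.1 is similar for haematology. On the laboratory, Protocol 8.3 says: "Laboratory samples will be processed centrally and the results will be sent electronically to Novartis".

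Protocol 4.1 sets two washouts of the same length as the footnote's look-back: "Last steroid dose of the patient should be at least 1 month before study entry" and "Last interferon or glatiramer acetate dose of the patient should be at least 1 month before study entry". There is no separate screening visit. Under Protocol 6.1, "The investigators will assess the inclusion/exclusion criteria in visit 1", so study entry is taken here as Visit 1, Day 0.

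SAP 6.3.1 takes 12 chemistry variables, "compared as Visit 1 vs. Visit 2 and Visit 1 vs. Visit 3 by using appropriate statistical test". SAP 6.3.2 does the same for five haematology variables: "WBC, Absolute Lymphocyte Count, Platelet, Absolute Neutrophil Count and Hemoglobin". The tests are paired t or Wilcoxon. The SAP does not define a laboratory baseline, has no rule for results carried in from before Visit 1, and plans no sensitivity analysis without them.

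**The concern.** A paired test of baseline against follow-up reads the difference as change on study treatment. That reading needs the baseline to describe the patient just before the first dose. A Day 0 draw guarantees at least one month off steroids, interferon and glatiramer acetate. A reused result carries no such guarantee, because the look-back can use up the whole washout. Any residual effect of the previous drug on blood counts, liver enzymes or glucose would then sit in the baseline and appear, with the opposite sign, as change on fingolimod. The footnote also does not ask that the reused result come from the laboratory that runs Visits 2 and 3, so a difference between laboratories could enter the same contrast.

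The protocol itself treats recent steroids as a reason to delay a study sample: section 5.4.6 asks for a one-month gap between a corticosteroid course and the blood sample. That passage reads most naturally as meaning the biomarker sample, but the reasoning carries over. Among the affected variables is the lymphocyte count, whose reduction is one of the pharmacodynamic effects listed in Protocol 1.1.

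**Working it through.** The plan states no figure on this point, so there is nothing to reproduce. The check sets the time windows against each other and then asks what a shifted baseline does to a paired test.

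**1. Gap between last dose and baseline sample.** Let W be the time from the last dose of prior therapy to Visit 1, and L the age of the laboratory result at Visit 1. The gap is W − L.
- Protocol 4.1: W ≥ 1 month for steroids, interferon and glatiramer acetate.
- Table 6-1 footnote: L ≤ 1 month.
- Day 0 draw (L = 0): gap ≥ 1 month.
- Reused result: smallest gap = 1 − 1 = 0 months.
- A reused result falls short of one month's washout only if W − L < 1, that is W < 1 + L, so W must be under 2 months. With W of 2 months or more, the gap is at least one month whatever is reused.
- For drugs with the three-month washout, the gap is at least 3 − 1 = 2 months.

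**2. Comparisons exposed.** (12 chemistry + 5 haematology) × 2 contrasts = 34 paired tests, which is all of SAP 6.3 and nothing outside it. In Table 6-1 the biomarker samples, EDSS, PASAT, SDMT, peg test and walk test have no reuse footnote.

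**3. Interval between the paired samples** (visit windows 90 ± 7 and 180 ± 14 days, one month taken as 31 days).

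| Contrast | Day 0 draw | Longest with reuse |
|---|---|---|
| Visit 1 to Visit 2 | 83–97 days | 97 + 31 = 128 days |
| Visit 1 to Visit 3 | 166–194 days | 194 + 31 = 225 days |

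The extra days all fall before treatment. Time since first dose is unchanged.

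**4. Bias.** If a share q of patients have a reused baseline that differs on average by d from their true Day 0 value, the mean change is off by q × d in size, with sign opposite to d. The documents give neither q nor d.

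**5. Illustration under assumed values.** Take n = 60 (the enrolment minimum in Protocol 9.8), a two-sided 5% paired t test and no true change. Let the shift be s standard deviations of the paired difference. The noncentrality is q × s × √n. For q = 0.5 and s = 0.3 it is 0.15 × 7.75 = 1.16.

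| Share reused (assumed) | s = 0.2 | s = 0.3 | s = 0.5 |
|---|---|---|---|
| 25% | 7% | 9% | 16% |
| 50% | 12% | 21% | 48% |

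Entries are rejection rates against a nominal 5%. They ignore the extra spread from mixing reused and fresh baselines, which is at most 0.5 × 0.5 × 0.5² = 0.0625 on a variance of 1. The table shows how sensitive the test is to q and s. It is not an estimate for this trial.

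**The case against.** The strongest reply is that little depends on this. The objectives concern cytokines, chemokines and clinical scales, and Protocol 6.5 says no safety analysis is planned. With eligibility and first dose both at Visit 1, accepting a recent result is a sensible operational choice, and the footnote can be read as a specific exception to the general schedule in 6.5.1.2. All of that stands. It limits the importance of the point but does not remove it, because the SAP still commits to the 34 tests and does not say what their baseline is.

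Several stronger readings are tempting and go beyond the documents:
- **Every Visit 2 and Visit 3 comparison is compromised.** Only SAP 6.3 is exposed.
- **Baselines were drawn on the day of the last dose.** That is the boundary case: minimum washout together with maximum look-back. Previously untreated patients are eligible and have no interferon to wash out. Steroids given for a relapse are further constrained by the two-month relapse-free requirement in Protocol 4.1.
- **The laboratory changes between visits.** Section 8.3 is a general statement, and the central laboratory named in 6.5.1 is tied to flow cytometry. Routine bloods may be local throughout, so a change of laboratory is possible but not documented.
- **Reuse is selective**, favouring patients recently monitored on earlier therapy. This is plausible, but nothing in the documents shows it.
- **Lymphocyte reduction is the main effect and needs a same-day biomarker baseline.** Protocol 1.1 lists three pharmacodynamic effects without ranking them, and no planned analysis links lymphocyte counts to cytokine levels.

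It is also an inference, from the mark in the Visit 1 column, that an old result is entered as the Visit 1 value. If it is not entered, those patients have no laboratory baseline, and the SAP needs a rule for that instead.

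**Conclusion.** The point holds in a limited form. The look-back and the minimum washout are both one month, so the plan permits a laboratory baseline taken close to the end of prior therapy, and the SAP analyses it as if it were a pre-dose study sample. The exposure is 34 supporting laboratory tests. Within them, the washout problem can arise only for patients who had steroids, interferon or glatiramer acetate less than two months before Visit 1 and whose result was reused. The primary and secondary objectives are not affected.

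Whether any comparison would be materially distorted cannot be settled from the documents, since the share reused and the size and direction of any shift are not given. The conclusion assumes that study entry means Visit 1 and that reused results are recorded as Visit 1 values. This is a minor point, worth acting on because the remedy costs so little.

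**What to change.** Amend the Table 6-1 footnote so that a result from the previous month may support the eligibility check only. Draw the scheduled Visit 1 haematology and chemistry panel from every patient on Day 0 before the first dose, in the same laboratory as Visits 2 and 3. In SAP 6.3, define that sample as the laboratory baseline. Align Protocol 6.5.1.1, 6.5.1.2 and 8.3 with the footnote, and state which laboratory handles the routine bloods.

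The cost is one routine panel for patients who would otherwise have skipped it, taken from the Visit 1 blood draw already planned for biomarkers, plus one line in the table and one in the SAP.

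If the footnote stays as it is, record the sample date and laboratory of each reused result, state in the SAP whether it counts as Visit 1, and repeat the SAP 6.3 paired tests without reused baselines as a sensitivity analysis. That needs no new collection. Its price is a somewhat smaller number of patients in the sensitivity analysis.

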**Table 6-2 Assessment schedule for Healthy Control Group**

Visit	1	2	3
Day	0	90±7	180±14
Obtain Informed Consent	X		
Evaluation of Inclusion/Exclusion Criteria	X		
Collecting Serum and Blood Samples	X		

Patients should be seen for all visits on the designated day with an allowed “visit window” of “7” days at visit 2 and “14” days at visit 3 , or as close to it as possible, or as shortly after it as possible, or as shortly before it as possible, etc.

At a minimum, patients will be contacted for safety evaluations during the 30 days following the last study visit or following the last administration of study treatment if there are post-treatment follow-up visits (whichever is later), including a final contact at the 30-day point. Documentation of attempts to contact the patient should be recorded in the source documentation.

## **6.1 Information to be collected on screening failures**

Since the study is aiming to collect serum samples from the MS patients and healthy volunteers, screening visit is not applicable. The investigators will assess the inclusion/exclusion criteria in visit 1 and the patients who are not eligible for the study will not give any serum samples. There is no information to be collected for screen failures.

## **6.2 Patient demographics/other baseline characteristics**

Data of patient demographics and baseline characteristics will be collected from all patients that include: date of birth and sex. Relevant medical history/current medical condition data includes data until the start of study drug. If there is, concomitant diseases will be recorded. In addition, MS history and MS treatment will be recorded.

At Visit 1, an ECG will be performed to ensure that the patients continue to meet inclusion criteria prior to taking the first dose of fingolimod. After 6 hours of the first dose, the ECG will be repeated. Should any of the cardiac inclusion criteria is met based on the ECG results, the patient will not be allowed to participate in the study. ECGs will be printed out and will be kept at the study site as a source document.

## **6.3 Treatment exposure and compliance**

In order to collect accurate information about the study drug exposure, the following records should be maintained for each patient: records of study medication dispensed and returned, dosages administered and intervals between visits.

Compliance will be assessed by the investigator and/or study personnel at each visit using capsule counts and information provided by the patient. A monitor will perform and document drug accountability during site visits and at the end of the study.

Patients who discontinue study medication for 1 month totally will be considered withdrawn.

## **6.4 Efficacy**

General definition of relapse: Appearance of a new neurological abnormality or worsening of previously stable or improving pre-existing neurological abnormality, separated by at least 30 days from onset of a preceding clinical demyelinating event. The abnormality must be present for at least 24 hours and occur in the absence of fever (<37.5C) or infection.

### Severity of MS relapse

Mild relapse	Moderate relapse	Severe relapse
EDSS increase of 0.5 point	EDSS increase of 1 or 2 points	Exceeding Moderate criteria
Or	or	or
1 point FS change in one to three systems	2-point FS change in one or two systems	Exceeding Moderate criteria
	or	or
	1-point change in four or more systems	Exceeding Moderate criteria

|Reference: Panitch, H (2002)

### Expanded Disability Status Scale (EDSS)

EDSS is a scale for assessing neurologic impairment in MS (Kurtzke 1983) including (1) a series of scores in each of eight functional systems, and (2) the EDSS steps (ranging from 0 (normal) to 10 (death due to MS). The functional systems are Visual, Brain Stem, Pyramidal, Cerebellar, Sensory, Bowel & Bladder, Cerebral and Other functions. It is recommended that fatigue is not included in the Cerebral score of the EDSS.

EDSS will be assessed by the investigator at each site, who has successfully completed his/her certification requirements. EDSS assessments are scheduled at baseline and at the end of the 6 monthly treatments on Visit 3.

#### **6.4.1 Efficacy assessment**

MS Relapses and EDSS is the key efficacy assessment criteria. Efficacy assessment will be performed at the end of the study.

#### **6.4.2 Appropriateness of efficacy assessments**

Measurements are the standard key efficacy criteria for MS.

### **6.5 Safety**

This study does not include any planned safety analysis.

#### **6.5.1 Laboratory evaluations**

Blood samples will be collected from each patient and healthy control after evaluation for inclusion and exclusion criteria. Additional blood samples at 2 different time points will be collected from MS patients at months 3 ( $\pm 1$  week) and 6 ( $\pm 2$  weeks) after starting fingolimod 0.5 mg/day po. treatment. Serum samples will be sent to the central laboratory (DETAE) for flow cytometry assay on the same day they are collected. Serum samples will be stored at -20°C at local centers for a longest duration of two week and kept frozen at -80°C [REDACTED]

The levels of IL-4, IL-6, IL-8, IL-9, IL-10, IL-13, IL-17, IL-23, IFN- $\gamma$ , TNF- $\alpha$ , VLA4, CCL2, CCL5, CXCR3, CXCL13 will be measured by ELISA according to the manufacturer's protocols. Optical density (OD) will be measured at 450 nm and cytokine/chemokine concentrations (pg/ml) will be calculated by referring to a standard curve.

In order to perform the flow cytometry assay freshly purified peripheral blood mononuclear cells (PBMC) from venous blood will be stimulated for 24 h by a combination of phorbol ester (PMA, 50 ng/ml) and Ca2+ Ionophore (Ionomycin, 250 ng/ml). The combination of these two stimuli will be used to achieve the strongest stimulus for intracytoplasmic cytokine secretion. Monensin will be added at a final concentration of 1 mM. After stimulation, the cells will be washed with PBS and will be stained with anti-CD4, anti-CD8, anti-CD25, and then fixed and permeabilized. After washing with PBS, the cells will be stained with PE-conjugated anti-IL-4, anti-IL-6, anti-IL-9, anti-IL-10, anti-IL-13, anti-IL-17, anti-IFN- $\gamma$ , anti-TNF- $\alpha$  for 30 min at room temperature and analyzed by flow cytometry.

Cytokine and chemokine levels will be analyzed cumulatively at the end of the study. The results will be recorded to the blood sampling logs and laboratory logs cumulatively.

#### **6.5.1.1 Hematology**

Hematology parameters will be collected at screening and each scheduled visit and will include: WBC count, absolute lymphocytes, platelet, absolute neutrophil count, and hemoglobin.

#### **6.5.1.2 Clinical chemistry**

Blood samples will be collected at screening (Visit 1) and at each scheduled visit to verify a patient's eligibility and will include but not limited to the following parameters: AST, ALT, BUN, Creatinine, Total Cholesterol, Tryglicerides, LDL-K, HDL-K, TSH, ST4, Glucose, HbA1c

#### **6.5.2 Electrocardiogram (ECG)**

A standard 12 lead ECG will be performed at baseline. The ECG will be performed before the intake of the first dose of the study drug and after 6 hours of the intake of the study drug. Interpretation of the tracing must be made by a qualified physician and documented on the ECG section of the CRF. Each ECG tracing should be labeled with the study and subject number, date, and kept in the source documents at the study site. Clinically significant abnormalities should also be recorded on the Medical History/Adverse event CRF page. Clinically significant findings must be discussed with the Novartis Medical Monitor prior to enrolling the patient in the study.

#### **6.5.3 Optical Cohorence Tomography (OCT)**

An optical coherence tomography for the eyes will be performed in the baseline and in Visit 2. The tracing of the OCT must be made by a qualified physician and documented on the OCT section of the CRF. Each OCT tracing should be labeled with the study and subject number, date, and kept in the source documents at the study site. Clinically significant abnormalities

should also be recorded on the Medical History/Adverse event CRF page. Clinically significant findings must be discussed with the Novartis Medical Monitor prior to enrolling the patient in the study.

#### **6.5.4      Pregnancy and assessments of fertility**

All pre-menopausal women who are not surgically sterile will have a urine pregnancy test. A positive urine pregnancy test requires immediate interruption of study drug until serum  $\beta$ -hCG is performed and found to be negative. If positive, the patient must be discontinued from the trial.

#### **6.5.5      Appropriateness of safety measurements**

The safety assessments selected are standard for this indication/patient population.

### **6.6      Other assessments**

For clinical measures; EDSS and relapses will be recorded after 6 months of treatment. EDSS scoring will also be performed at study entry. PASAT, 9-Hole Peg test, timed 25-foot walk and SDMT tests will be performed only at study entry and termination after 6 months.

